7 TRIAL PROCEDURES

Details of analysis of blood & urine samples

The aim of the analysis of the study samples will be to: (i) show the dose-dependent effects of aspirin on the immune response to endotoxaemia including on inflammatory markers, cytokines, prostanoids, leucocytes, haemostasis and platelet function, and (ii) show whether the addition of ticagrelor modifies these effects.

We will measure inflammatory markers and cytokines that include, but are not limited to, TNF α , IL-6 and CRP.

To determine the detailed effects of aspirin dose modification on circulating prostanoids in the unstimulated and endotoxin-stimulated states, we will measure a panel of eicosanoids and/or their metabolites, including, but not limited to, PGE₂, PG_I₂ and TXB₂ and will additionally assess the effect of ticagrelor on endotoxin-induced responses.

Haemostasis will be assessed by measuring bleeding time pre- and 3 hours post-endotoxin using a method shown to be sensitive to additive effects of antiplatelet agents [33]. The procedure for measuring bleeding time is described in the study-specific SOP relating to this.

Finally, in order to confirm the efficacy of the antiplatelet aspects of the drug regimens being studied, the activity of a broad range of pathways of platelet activation and aggregation will be assessed by light transmittance aggregometry pre-medication, post-medication at peak inflammation and during the resolution phase of inflammation, using arachidonic acid 0.3 and 1 mmol/l, collagen 4 and 16 µg/ml, and ADP 20 µmol/l as agonists.

Study samples will either be measured immediately after collection (eg. light transmittance aggregometry) or stored for assays at a later time (other endpoints).

We will also store acellular samples of serum, plasma, deoxyribonucleic acid (DNA), ribonucleic acid (RNA) and urine within the Cardiovascular Research Unit for future, as yet unplanned, studies. Consent will be sought for this at study enrolment.

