16. Serum TXB₂ over time following endotoxin administration (measured at 0, 0.5, 1, 1.5, 2, 3, 4 and 6 hours post-endotoxin) assessed between aspirin groups (control vs. 20 mg BD vs. 75 mg OD vs. 300 mg OD, given in combination with ticagrelor) by two-way mixed ANOVA with treatment as a between-subjects factor and timepoint as a within-subjects factor.
17. Urinary PGI-M (measured at 0, 2, 4 and 6 hours, each adjusted for [divided by] urinary creatinine) over time following endotoxin administration assessed between aspirin groups (control vs. 20 mg BD vs. 75 mg OD vs. 300 mg OD, given in combination with ticagrelor) by two-way mixed ANOVA with treatment as a between-subjects factor and timepoint as a within-subjects factor.
18. Serum PGE₂ over time following endotoxin administration (measured at 0, 0.5, 1, 1.5, 2, 3, 4 and 6 hours post-endotoxin) assessed between aspirin groups (control vs. 20 mg BD vs. 75 mg OD vs. 300 mg OD, given in combination with ticagrelor) by two-way mixed ANOVA with treatment as a between-subjects factor and timepoint as a within-subjects factor.
19. Circulating leukocyte count over time following endotoxin administration (measured at 0, 0.5, 1, 1.5, 2, 3, 4 and 6 hours post-endotoxin) assessed between aspirin groups (control vs. 20 mg BD vs.

75 mg OD vs. 300 mg OD, given in combination with ticagrelor) by two-way mixed ANOVA with treatment as a between-subjects factor and timepoint as a within-subjects factor.

20. AUC of the graph of bleeding time following endotoxin administration (measured at 0 and 3 hours post-endotoxin) assessed between aspirin groups (control vs. 20 mg BD vs. 75 mg OD vs. 300 mg OD, given in combination with ticagrelor) by one-way mixed ANOVA.
21. AUC of the graphs of platelet aggregation to arachidonic acid (0.3 and 1 mmol/L), collagen (4 and 16 µg/ml) and ADP (20 µmol/L) over time following endotoxin administration (measured at 0 and 3 hours post-endotoxin) assessed between aspirin groups (control vs. 20 mg BD vs. 75 mg OD vs. 300 mg OD, given in combination with ticagrelor) by one-way ANOVA.

To compare aspirin monotherapy with aspirin and ticagrelor in combination:

1. Plasma TNF- α at 2 hours following endotoxin administration) compared between each aspirin regimen (control, 20 mg BD, 75 mg OD, 300 mg OD, each without ticagrelor) and each corresponding DAPT regimen (control, 20 mg BD, 75 mg OD, 300 mg OD, each with ticagrelor 90 mg BD) by paired t-tests.

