BD, 75 mg OD, 300 mg OD, each without ticagrelor) and each corresponding DAPT regimen (control, 20 mg BD, 75 mg OD, 300 mg OD, each with ticagrelor 90 mg BD) by paired t-tests.

9. AUC of the graph of circulating leukocyte count over time following endotoxin administration (measured at 0, 0.5, 1, 1.5, 2, 3, 4 and 6 hours post-endotoxin) compared between each aspirin regimen (control, 20 mg BD, 75 mg OD, 300 mg OD, each without ticagrelor) and each corresponding DAPT regimen (control, 20 mg BD, 75 mg OD, 300 mg OD, each with ticagrelor 90 mg BD) by paired t-tests.
10. AUC of the graph of bleeding time following endotoxin administration (measured at 0 and 3 hours post-endotoxin) compared between each aspirin regimen (control, 20 mg BD, 75 mg OD, 300 mg OD, each without ticagrelor) and each corresponding DAPT regimen (control, 20 mg BD, 75 mg OD, 300 mg OD, each with ticagrelor 90 mg BD) by paired t-tests.
11. AUC of the graphs of platelet aggregation to arachidonic acid (0.3 and 1 mmol/L), collagen (4 and 16 µg/ml) and ADP (20 µmol/L) over time following endotoxin administration (measured at 0 and 3 hours post-endotoxin) compared between each aspirin regimen (control, 20 mg BD, 75 mg OD, 300 mg OD, each without ticagrelor) and each corresponding DAPT regimen (control, 20 mg BD, 75 mg OD, 300 mg OD, each with ticagrelor 90 mg BD) by paired t-tests.

And to model the effects of all variables (considering parallel groups):

12. Plasma TNF-α over time following endotoxin administration (measured at 0, 0.5, 1, 1.5, 2, 3, 4 and 6 hours post-endotoxin) compared between each aspirin regimen (control, 20 mg BD, 75 mg OD, 300 mg OD, each without ticagrelor) and each corresponding DAPT regimen (control, 20 mg BD, 75 mg OD, 300 mg OD, each with ticagrelor 90 mg BD) with a mixed three-way ANOVA with aspirin-dose and presence or absence of ticagrelor as between-subjects factors and timepoint as a within-subject factor.
13. Plasma IL-6 over time following endotoxin administration (measured at 0, 0.5, 1, 1.5, 2, 3, 4 and 6 hours post-endotoxin) compared between each aspirin regimen (control, 20 mg BD, 75 mg OD, 300 mg OD, each without ticagrelor) and each corresponding DAPT regimen (control, 20 mg BD, 75 mg OD, 300 mg OD, each with ticagrelor 90 mg BD) with a mixed three-way ANOVA with aspirin-dose and presence or absence of ticagrelor as between-subjects factors and timepoint as a within-subject factor.

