19. Bleeding time following endotoxin administration (measured at 0 and 3 hours post-endotoxin) compared between each aspirin regimen (control, 20 mg BD, 75 mg OD, 300 mg OD, each without ticagrelor) and each corresponding DAPT regimen (control, 20 mg BD, 75 mg OD, 300 mg OD, each with ticagrelor 90 mg BD) with a mixed three-way ANOVA with aspirin-dose and presence or absence of ticagrelor as between-subjects factors and timepoint as a within-subject factor.
20. Platelet aggregation to arachidonic acid (0.3 and 1 mmol/L), collagen (4 and 16 µg/ml) and ADP (20 µmol/L) over time following endotoxin administration (measured at 0 and 3 hours post-endotoxin) compared between each aspirin regimen (control, 20 mg BD, 75 mg OD, 300 mg OD, each without ticagrelor) and each corresponding DAPT regimen (control, 20 mg BD, 75 mg OD, 300 mg OD, each with ticagrelor 90 mg BD) with a mixed three-way ANOVA with aspirin-dose and presence or absence of ticagrelor as between-subjects factors and timepoint as a within-subject factor.

For all endpoints (primary and secondary) tested with ANOVA, pairwise comparisons with Bonferroni correction will be used to explore relationships further where the prespecified test suggests significant differences between the groups (p<0.05).

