Additionally, continuing the study will be considered futile, and therefore discontinued, if the lower limit of the 95 % confidence interval of the mean change in TNF- α at 2 hours after endotoxin from the 300 mg aspirin OD group to no aspirin group is less than (more negative than) -2000 pg/mL.

Should neither of these criteria be met, the investigators will meet to review the results of the interim analysis and, in discussion with the Sponsor, decide on whether to continue the study, taking into account feasibility, including consideration of local and national restrictions.

Secondary analyses to be carried out in the event of premature termination

If the trial is prematurely terminated, data concerning other endpoints will then be analysed as follows, using methods taking best into account the cases of participant data missing from one period:

1. Plasma TNF- α over time following endotoxin administration (measured at 0, 0.5, 1, 1.5, 2, 3, 4 and 6 hours post-endotoxin) assessed between treatment groups (control vs. 20 mg BD vs. 75 mg OD vs. 300 mg OD, with or without ticagrelor) using a mixed effect linear model with patient as a random effect, aspirin dose, presence or absence of ticagrelor treatment and treatment period (first or second) as fixed effects, and baseline value as covariate.
2. Plasma IL-6 over time following endotoxin administration (measured at 0, 0.5, 1, 1.5, 2, 3, 4 and 6 hours post-endotoxin) assessed between treatment groups (control vs. 20 mg BD vs. 75 mg OD vs. 300 mg OD, with or without ticagrelor) using a mixed effect linear model with patient as a random effect, aspirin dose, presence or absence of ticagrelor treatment and treatment period (first or second) as fixed effects, and baseline value as covariate.
3. Change in serum CRP over time following endotoxin administration (measured at 0 and 6 hours post-endotoxin) assessed between treatment groups (control vs. 20 mg BD vs. 75 mg OD vs. 300 mg OD, with or without ticagrelor) using a mixed effect linear model with patient as a random effect, aspirin dose, presence or absence of ticagrelor treatment and treatment period (first or second) as fixed effects, and baseline value as covariate.

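### The aim of showing whether ticagrelor modifies the aspirin-dose effects has no named interaction test with a within-person error term

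*Protocol*

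**What the plan says.** Protocol section 7 gives two aims for the sample analysis. The second is to "show whether the addition of ticagrelor modifies these effects", meaning the dose-dependent effects of aspirin. Under sections 4 and 7.3 each participant keeps one aspirin regimen (or none) in both periods and receives ticagrelor in one period only, so ticagrelor varies within person and aspirin dose varies between people.

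Three sets of planned analyses involve both treatments. The wording is the same in the Protocol and the SAP.

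- **Paired t-tests** (section 10.3.3, monotherapy against combination, items 1 to 11). Each marker is "compared between each aspirin regimen (control, 20 mg BD, 75 mg OD, 300 mg OD, each without ticagrelor) and each corresponding DAPT regimen", giving four tests per marker. The Bonferroni rule that closes the section applies to endpoints tested with ANOVA. No rule is given for the t-tests.
- **Three-way ANOVA** (same section, items 12 to 20), introduced by "And to model the effects of all variables (considering parallel groups". The factors are "aspirin-dose and presence or absence of ticagrelor as between-subjects factors and timepoint as a within-subject factor".
- **Early-termination mixed models** (section 10.6). Participant is a random effect, with "aspirin dose, presence or absence of ticagrelor treatment and treatment period (first or second) as fixed effects" and baseline value as covariate.

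**The concern.** Whether ticagrelor modifies the aspirin effect is a question about the dose by ticagrelor interaction: does the with-minus-without difference vary across the four aspirin groups? The crossover supplies that difference for every participant, free of between-person variation.

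The planned analyses do not use it in that way. The t-tests estimate the difference inside each group and stop there. A significant result at one dose and a non-significant one at another would not show that the two doses differ. The three-way ANOVA could yield an interaction, but with an error term that includes the between-person variation the design removes. The early-termination models have a suitable structure but list main effects only. At stake is whether the crossover half of the trial can answer one of its two stated aims.

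**Working it through.** **The plan's own figure first.** Protocol section 10.1 gives variance of means V = 0.031, SD 0.410, four groups and 16 per group. With λ = n·G·V/s² = 16 × 4 × 0.031 / 0.1681 = 11.80 on 3 and 60 df, power is 80.6%, so the stated 16 per group reproduces. Natural logs of 1, 1.2, 1.4 and 1.6 give V = 0.0307 and 80.2%, which supports reading the SD as natural-log.

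**Assumptions.** The documents give no ticagrelor effect and no within-person correlation ρ. I take ρ = 0.3, 0.5 and 0.7, one timepoint, 16 per aspirin group and two-sided 0.05. For the interaction, ticagrelor exactly cancels the +20%, +40% and +60% aspirin effects, so its effects on the log scale are 0, −0.182, −0.336 and −0.470, again with V = 0.0307. Period effects are left out.

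**Interaction on within-person differences.** The SD of a difference is 0.41 × √(2(1−ρ)), and λ = 64 × 0.0307 / SD² on 3 and 60 df. At ρ = 0.5 this SD is 0.41, so the power equals that of the primary analysis.

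**Interaction as written.** If both periods enter an eight-cell between-subjects layout, the interaction mean square has expectation σ²(1−ρ) when there is no interaction, but it is divided by an error mean square with expectation σ². F is therefore too small by a factor of about 1−ρ. Power and type I error come from simulation (20,000 trials).

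| ρ | SD of difference | λ | Power, within-person | Power, as written | Type I error, as written |
|---|---|---|---|---|---|
| 0.3 | 0.485 | 8.36 | 64% | about 44% | about 1% |
| 0.5 | 0.410 | 11.70 | 80% | about 38% | about 0.1% |
| 0.7 | 0.318 | 19.50 | 96% | about 31% | about 0% |

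The within-person test holds its level (4.7% to 5.0% in simulation). A noncentral F for eight independent cells gives 49% (λ = 64 × 0.0307 / (2 × 0.1681) = 5.85), but that is the ρ = 0 case and does not describe paired data.

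**If the three-way model uses period 1 only.** Ticagrelor is then truly between-subjects, with 16/2 = 8 per cell. λ = 32 × 0.0307 / (2 × 0.1681) = 2.93 on 3 and 56 df, and power is about 25%.

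**How often four t-tests disagree when ticagrelor has the same effect at every dose.** With power p per test, the chance that some but not all are significant is 1 − p⁴ − (1−p)⁴.

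| Uniform reduction | p at ρ = 0.3 / 0.5 / 0.7 | Mixed verdict |
|---|---|---|
| none | 5% | 18.5% |
| 20% | 41% / 53% / 75% | 85% / 87% / 68% |
| 30% | 78% / 90% / 99% | 62% / 34% / 5% |
| 40% | 98% / 99.6% / 100% | 9% / 1% / 0% |

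A mixed verdict is the majority outcome only when p lies between about 16% and 84%. If 0.41 were an SD of log10 values, the 20% row would be 39%, 46% and 61%.

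**The case against.** The t-tests are not given the job of testing effect modification. Their heading announces a comparison of monotherapy with combination, and they carry out the within-regimen comparisons listed in Protocol section 3.3. A paired t-test is an ordinary choice for that. Section 3.3 also lists a comparison of all eight regimens, and a full-factorial three-way ANOVA would contain the interaction. All of this stands, and it rules out several stronger readings.

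- A reader might infer that the plan judges modification by the four t-tests. No text says so. The gap is that no text names any test for it.
- A reader might infer that a split verdict across doses is the usual result. The documents give no ticagrelor effect from which to say so. The split is common for a uniform 20% reduction and rare for 40%.
- A reader might infer that the three-way ANOVA yields false interactions, or that no valid test exists. Used on both periods it is conservative, and on period 1 alone it is valid but weak.
- A reader might infer that the three-way ANOVA is the only model with both factors. The section 10.6 models also have both, keep the pairing and adjust for period. What they lack is the interaction.

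These are also secondary analyses, and the primary comparison excludes ticagrelor. That limits the weight of the point but does not remove it, because they carry a stated aim.

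**Conclusion.** The concern holds in this form: no planned analysis tests effect modification with the right error term. The t-tests do not address it. The three-way ANOVA uses a between-subjects error term for a within-person factor and does not cover TNF-α and IL-6 at 2 hours as endpoints in their own right. The early-termination models list no dose by ticagrelor term.

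Under the stated assumptions the cost is a fall in interaction power from 64%, 80% or 96% to about 44%, 38% or 31%, or to about 25% if only period 1 is used. The gap widens as the correlation rises, that is, as the crossover becomes more informative. The exact figures depend on the assumed correlation, the full-cancellation effect and the natural-log SD. The direction follows from the error term. The change should be made, but it does not affect the primary analysis.

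**What to change.** For each marker, and for the 2-hour TNF-α and IL-6 values as separate endpoints:

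1. Replace the between-subjects three-way ANOVA with the mixed model already written in section 10.6 (participant random, treatment period fixed).
2. Add the aspirin dose by ticagrelor interaction. For markers measured over time, include timepoint and its interactions, since section 10.6 does not list timepoint as a model term.
3. Name that interaction as the test of the second aim, in both the full and the early-termination analyses.
4. Report the four within-group ticagrelor effects as estimates with confidence intervals, not as four separate verdicts.

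A one-way ANOVA of within-person differences, with treatment order as a factor, would also use the right error term, but only for complete pairs. Section 10.6 expects 46 participants with a first endotoxin day and 37 with both, so 46 − 37 = 9 would be lost. The mixed model keeps them.

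The cost is SAP wording and one model term per marker. No new data are needed.

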Period 1: Day 1 - Day 10 (to 14)

- Participants will receive one of the following antiplatelet medication regimens for 10 to 14 days:
 - No IMP
 - No aspirin but a loading dose of ticagrelor (180 mg) taken on the last day of the medication period, 1 hour prior to endotoxin injection
 - Aspirin (aspirin lysine) 20 mg BD (only)
 - Aspirin (aspirin lysine) 20 mg BD, and a loading dose of ticagrelor (180 mg) taken on the last day of the medication period, 1 hour prior to endotoxin injection
 - Aspirin (aspirin lysine) 75 mg OD (only)

- Aspirin (aspirin lysine) 75 mg OD, and a loading dose of ticagrelor (180 mg) taken on the last day of the medication period, 1 hour prior to endotoxin injection
- Aspirin (aspirin lysine) 300 mg OD (only)
- Aspirin (aspirin lysine) 300 mg OD, and a loading dose of ticagrelor (180 mg) taken on the last day of the medication period, 1 hour prior to endotoxin injection

Visit 3 - Period 1: Day 11 (to 15)

On arrival

- Vital signs
- Physical examination
- Adverse event recording
- Concomitant medication recorded
- IMP compliance check for period 1
- Medically-qualified member of the research team to confirm that the withdrawal criteria (section 7.10) are not met, prior to proceeding further with visit

-1 hour (1 hour before endotoxin injection)

- IV cannula insertion (x2, one in each arm)
- 35.5 ml venous blood sample for baseline lab safety (full blood count, urea & electrolytes [sodium, potassium, urea and creatinine], liver function tests, clotting screen), cytokines, prostanoids, inflammatory markers and platelet function
- Bleeding time measurement
- Urine sample for prostanoid assessment at baseline
- Receive last dose of aspirin of period 1, or last dose of aspirin plus a loading dose of ticagrelor (180 mg), or no IMP, as directed by randomisation allocation
- Collect unused study medication and perform drug accountability check (sachet/pill count)
- Infusion of 250 ml 0.9% saline over 30 minutes
- 23 ml venous blood at 60 minutes after last dose of oral antiplatelet medication or equivalent time if not receiving IMP during period 1 (just before endotoxin administration)

0 hour (time of endotoxin injection)

- Continuous cardiac monitoring starts
- *E.coli* endotoxin 2 ng/kg intravenously administered over 1 minute
- Vital signs at 5, 15 and 30 minutes post-endotoxin
- Continuous IV infusion of 250 ml 0.9% saline over 1 hour
- 14 ml venous blood sample at 30 minutes post endotoxin

1 hour post endotoxin injection

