- Vital signs at 1 hour and 1.5 hours post endotoxin injection
- Continuous IV infusion of 250 ml 0.9% saline over 1 hour
- 14 ml venous blood sample at 1 hour post endotoxin
- Urine sample at 1 hour post endotoxin
- 14 ml venous blood sample at 1½ hours post endotoxin

2 hours post-endotoxin injection

- Vital signs at 2 hours post endotoxin
- Continuous IV infusion of 250 ml 0.9% saline over 1 hour
- 23 ml venous blood sample at 2 hours post endotoxin
- Urine sample at 2 hours post endotoxin

3 hours post-endotoxin injection

- Vital signs at 3 hours post endotoxin
- 23 ml venous blood sample at 3 hours post endotoxin
- Bleeding time measurement at 3 hours post endotoxin

4 hours post-endotoxin injection

- Vital signs at 4 hours post endotoxin
- 14 ml venous blood sample at 4 hours post endotoxin
- Urine sample at 4 hours post endotoxin

6 hours post-endotoxin injection

- Vital signs at 6 hours post endotoxin
- 14 ml venous blood sample at 6 hours post endotoxin
- Urine sample at 6 hours post endotoxin
- Continuous cardiac monitoring ends

Visit 4 (Period 1, 1 day after visit 3)

- Telephone follow-up for adverse events
- Facility to convert to in-person visit if any concerns raised

There will then follow a washout period of at least 5 weeks, and not more than 18 weeks, between the first endotoxin challenge day and the beginning of the second medication period. This is to avoid reliably any tolerance of the response to endotoxin, a phenomenon absent by 5 weeks [39].

Visit 5 (10 to 14 days after visit 3)

- Telephone follow-up for adverse events

Visit 6 (Period 2, Day 0)

- Vital signs (BP, pulse, temperature)
- Physical examination
- Adverse event recording
- Concomitant medication recording
- Medically qualified investigator to confirm eligibility criteria again (see section 6) and that no withdrawal criteria (section 7.10) are met at this point prior to proceeding to medication period 2
- Laboratory safety blood tests: 12.5 ml venous blood for full blood count, urea & electrolytes (sodium, potassium, urea and creatinine), liver function tests, clotting screen
- Medication dispensed for period 2
- Dosing training for use of aspirin lysine if required

Participants will be advised to begin antiplatelet medication, allocated as follows, for period 2 from the morning after visit 6:

- If received no IMP in period 1, to receive no aspirin, but a loading dose of ticagrelor (180 mg) 1 hour before endotoxin injection in period 2.

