- **Prostanoids and Leukotrienes**
- Serum TXB₂: Baseline, pre-last medication dose, pre-endotoxin and 0.5, 1, 1.5, 2, 3, 4 and 6 hours post-endotoxin
- Urinary PGI-M: Baseline, pre-endotoxin and 1, 2, 4 and 6 hours post-endotoxin
- Urinary creatinine: Baseline, pre-endotoxin and 1, 2, 4 and 6 hours
- Serum PGE₂: Baseline, pre-endotoxin and 0.5, 1, 1.5, 2, 3, 4 and 6 hours post-endotoxin
- **Leucocyte phenotype and activation status**
- White blood cell count with differential leukocyte count: Baseline, pre-last medication dose, pre-endotoxin and 0.5, 1, 1.5, 2, 3, 4 and 6 hours post-endotoxin
- **Haemostasis**
- Bleeding time: Pre-endotoxin and 3 hours post-endotoxin
- **Platelet function tests**
- Light transmittance aggregometry (agonists: arachidonic acid 0.3 and 1 mmol/l, collagen 4 and 16 mg/ml, and ADP 20 μ mol/l): Baseline, pre-endotoxin and 3 hours post-endotoxin
- **Samples for storage**
- Plasma for storage: Baseline, pre-last medication dose, pre-endotoxin and 0.5, 1, 1.5, 2, 3, 4 and 6 hours post-endotoxin
- Serum for storage: Baseline, pre-last medication dose, pre-endotoxin and 0.5, 1, 1.5, 2, 3, 4 and 6 hours post-endotoxin
- DNA/RNA for storage: Baseline
- Urine for storage: Baseline, pre-endotoxin and 1, 2, 4 and 6 hours post-endotoxin

Details of fluid management

We anticipate that the total fluid load per volunteer will be 1000 ml over the 8 hours of the day at the NGH-CRF (250 ml preload and 750 ml infusion). The volunteers will also receive fluid boluses if required, which would be typically be in the range of 250-500 ml normal saline, given if mean arterial blood pressure is reduced by 20% or more or to maintain a systolic blood pressure over 100 mmHg and/or to relieve symptoms related to hypotension. Under normal circumstances, we would give a maximum of 1000 ml of

0.9% saline over 1 hour and a maximum of 2000 ml of 0.9% saline over the 8 hours of the day at the NGH-CRF.

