8. Circulating leukocyte count over time following endotoxin administration (measured at 0, 0.5, 1, 1.5, 2, 3, 4 and 6 hours post-endotoxin) assessed between aspirin groups (control vs. 20 mg BD vs. 75 mg OD vs. 300 mg OD, without ticagrelor) by two-way mixed ANOVA with treatment as a between-subjects factor and timepoint as a within-subjects factor.

9. AUC of the graph of bleeding time following endotoxin administration (measured at 0 and 6 hours post-endotoxin) assessed between aspirin groups (control vs. 20 mg BD vs. 75 mg OD vs. 300 mg OD, without ticagrelor) by one-way ANOVA.
10. AUC of the graphs of platelet aggregation to arachidonic acid (0.3 and 1 mmol/L), collagen (4 and 16 µg/ml) and ADP (20 µmol/L) over time following endotoxin administration (measured at 0 and 6 hours post-endotoxin) assessed between aspirin groups (control vs. 20 mg BD vs. 75 mg OD vs. 300 mg OD, without ticagrelor) by one-way ANOVA.

Between DAPT regimens:

11. Plasma TNF- α at 2 hours following endotoxin administration assessed between aspirin groups (control vs. 20 mg BD vs. 75 mg OD vs. 300 mg OD, given in combination with ticagrelor) by one-way ANOVA with treatment as a factor.
12. Plasma TNF- α over time following endotoxin administration (measured at 0, 0.5, 1, 1.5, 2, 3, 4 and 6 hours post-endotoxin) assessed between aspirin groups (control vs. 20 mg BD vs. 75 mg OD vs. 300 mg OD, given in combination with ticagrelor) by two-way mixed ANOVA with treatment as a between-subjects factor and timepoint as a within-subjects factor.
13. Plasma IL-6 at 2 hours following endotoxin administration assessed between aspirin groups (control vs. 20 mg BD vs. 75 mg OD vs. 300 mg OD, given in combination with ticagrelor) by one-way ANOVA with treatment as a factor.
14. Plasma IL-6 over time following endotoxin administration (measured at 0, 0.5, 1, 1.5, 2, 3, 4 and 6 hours post-endotoxin) assessed between aspirin groups (control vs. 20 mg BD vs. 75 mg OD vs. 300 mg OD, given in combination with ticagrelor) by two-way mixed ANOVA with treatment as a between-subjects factor and timepoint as a within-subjects factor.
15. Change in serum CRP over time following endotoxin administration (measured at 0 and 6 hours post-endotoxin) assessed between aspirin groups (control vs. 20 mg BD vs. 75 mg OD vs. 300 mg OD, given in combination with ticagrelor) by one-way ANOVA.

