APPENDIX 1 Sample collection plan

Visit	Visit description	Timepoint within visit	Safety (FBC)	Safety (Chemistry)	Safety (Clotting screen)	DNA/RNA for storage	Plasma for cytokines/storage	Serum for prostaglandins/CRP /storage	Plasma for LTA	Blood for white cell count and subsets/storage	Total for timepoint	Urine	Bleeding time
		Tube type ↳	EDTA	SST	Citrate	EDTA	Citrate	SST	Citrate	Citrate			
Whole blood to draw (ml)													
1	Enrolment		4	4	4.5						12.5		
2	Randomisation			4	4	4.5		5	9	4.5	27	✓	✓
3	Endotoxin day 1	Baseline (pre drug dose)	4	4	4.5		4.5	5	9	4.5	35.5	✓	✓
	Post drug dose/pre endotoxin						4.5	5	9	4.5	23		
	30 mins post endotoxin						4.5	5		4.5	14		
	1 hour post endotoxin						4.5	5		4.5	14	✓	
	1.5 hours post endotoxin						4.5	5		4.5	14		
	2 hours post endotoxin						9	5		9	23	✓	
	3 hours post endotoxin						4.5	5	9	4.5	23	✓	
	4 hours post endotoxin						4.5	5		4.5	14	✓	
	6 hours post endotoxin						4.5	5		4.5	14	✓	
4	(Telephone call only)										0		
5	(Telephone call only)												
6	Start of period 2		4	4	4.5						12.5		
7	Endotoxin day 2	Baseline (pre drug dose)	4	4	4.5		4.5	5	9	4.5	35.5	✓	✓
	Post drug dose/pre endotoxin						4.5	5	9	4.5	23		
	30 mins post endotoxin						4.5	5		4.5	14		
	1 hour post endotoxin						4.5	5		4.5	14	✓	
	1.5 hours post endotoxin						4.5	5		4.5	14		
	2 hours post endotoxin						9	5		9	23	✓	
	3 hours post endotoxin						4.5	5	9	4.5	23	✓	
	4 hours post endotoxin						4.5	5		4.5	14	✓	
	6 hours post endotoxin						4.5	5		4.5	14	✓	
8	(Telephone call only)										0		
9	(Telephone call only)										0		
TOTAL			16	16	18	4	99	95	63	94.5	401		

EDTA, Ethylenediaminetetraacetic acid; LTA, light transmittance aggregometry; SST, serum separator tube. See main text of protocol for other abbreviations.

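### The two-point bleeding-time AUC averages a pre-ticagrelor value with the 3-hour value, so the planned paired comparison shows half of the 3-hour ticagrelor effect; some items also name a 6-hour time that is not sampled

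*Protocol*

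**What the plan says.** Protocol 3.3 defines secondary endpoint 8 as the bleeding-time AUC over 0 to 3 hours. The analyses are in 10.3.3 of both documents. The item numbers there run from 1 to 21 and then restart.

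- Second run, item 10 (monotherapy against combination with ticagrelor), by paired t-test: "AUC of the graph of bleeding time following endotoxin administration (measured at 0 and 3 hours post-endotoxin) compared between each aspirin regimen".
- Second run, item 19: three-way mixed ANOVA on the 0 and 3 hour values, with timepoint as a within-subject factor.
- First run, item 9 (aspirin regimens without ticagrelor): "AUC of the graph of bleeding time following endotoxin administration (measured at 0 and 6 hours post-endotoxin". Item 20 (regimens with ticagrelor) uses 0 and 3 hours.
- 10.6 item 8 (after early termination): mixed model on the 0 and 3 hour values with a baseline covariate.

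The collection schedule is in Protocol 7.7 and Appendix 1.

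- In the block for 1 hour before endotoxin at visits 3 and 7, "Bleeding time measurement" is listed above the dosing step: "Receive last dose of aspirin of period 1, or last dose of aspirin plus a loading dose of ticagrelor (180 mg), or no IMP".
- Appendix 1 marks urine and bleeding time in the row "Baseline (pre drug dose" and marks neither in the later row after dosing and before endotoxin.
- The only later value that day is "Bleeding time measurement at 3 hours post endotoxin". The investigation list agrees: "Bleeding time: Pre-endotoxin and 3 hours post-endotoxin".

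**The concern.** The analyses call the first value time 0, which suggests that it was taken under the full regimen at the moment of endotoxin. By the visit schedule, participants have at that point had 10 to 14 days of allocated aspirin but no ticagrelor. Ticagrelor is a single observed dose given in one period only, and the periods are at least 5 weeks apart. The first value therefore cannot carry a ticagrelor effect in either period. Averaging it with the 3-hour value shrinks the estimated effect and adds noise. Bleeding time is the only test listed under haemostasis in 7.7, and section 7 says that the method was chosen for its sensitivity to additive antiplatelet effects. The cost is an understated estimate and lost power. The test of no ticagrelor effect remains valid.

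**Working it through.** **Plan's own figure.** The documents give no effect size, SD or power for bleeding time. Their only calculation is for TNF-α in 10.1: four groups, effect size D² = 0.1828, alpha 0.05. The noncentral F distribution gives power 0.802 at 16 per group and 0.771 at 15, so the stated 16 is reproduced. Each aspirin regimen is crossed over with and without ticagrelor, so 16 per group also means 16 pairs in item 10.

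**Size of the effect in the AUC.** Let B0 be the pre-dose value and B3 the 3-hour value.

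1. Trapezoid rule: AUC(0–3) = 3 × (B0 + B3)/2.
2. Take within-person differences, with minus without ticagrelor. D0 has mean 0 and D3 has mean d.
3. Mean AUC difference = 3 × (0 + d)/2 = 1.5d. Divided by 3 hours this is d/2.

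**Precision.** Assume that D0 and D3 have the same SD, s, and correlation r.

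4. The SD of (D0 + D3)/2 is s × √((1+r)/2).
5. Standardised effect relative to D3 alone = (1/2)/√((1+r)/2) = 1/√(2(1+r)).
6. Ratio of pairs needed = 2(1+r).

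Take an effect with 80% power on the 3-hour value in 16 pairs (standardised effect 0.749, two-sided 0.05 assumed):

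| r (assumed) | Relative standardised effect | 2(1+r) | Power on the AUC, 16 pairs | Pairs for 80% on the AUC |
|---|---|---|---|---|
| 0 | 0.71 | 2.0 | 51% | 30 |
| 0.3 | 0.62 | 2.6 | 41% | 39 |
| 0.5 | 0.58 | 3.0 | 37% | 44 |
| 0.7 | 0.54 | 3.4 | 33% | 50 |

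The last column, from the noncentral t distribution, is slightly below 16 × 2(1+r) because the degrees of freedom rise with the number of pairs.

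**Simulation check.** In 60 simulated trials of 72 participants with a true 3-hour effect of 1.0, the paired AUC difference averaged 1.54 (expected 1.5). The 10.6 item 8 model, with both times as outcomes and the visit 2 baseline, gave a ticagrelor coefficient of 0.51. A model of the 3-hour value with that day's pre-dose value as covariate gave 0.98.

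**Time points.** No visit in 7.7 and no row in Appendix 1 has a bleeding time at 6 hours, yet item 9 of the first run uses one. Aggregation has the same mismatch. Item 10 of the first run and 10.6 item 9 use 0 and 6 hours, and endpoint 9 in 3.3 spans 0 to 6 hours, but the last aggregometry sample in 7.7 is at 3 hours. Unlike bleeding time, aggregometry does have a sample after dosing and before endotoxin in Appendix 1.

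**The case against.** **Is the first value really pre-dose?** Section 7.7 separates a sample before the last dose from one before endotoxin for TNF-α, IL-6, TXB₂ and leukocytes. Bleeding time has only the second label, which could mean after dosing. But urine carries the same label and is collected only before dosing. The order of the visit steps and the appendix row also both point to pre-dose. The appendix columns are not cleanly aligned in the text version, so its ticks corroborate the visit list and do not stand alone.

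**Is every bleeding-time analysis halved?** A reader might infer this, but the documents do not support it. In item 19 only the ticagrelor main effect is diluted; the ticagrelor-by-time interaction carries the full 3-hour effect. 10.6 item 8 is diluted if 0 hours is an outcome and baseline means visit 2. Section 7.7 defines baseline that way in its investigation list, but elsewhere it uses the word for the same-day pre-dose point. If the same-day value is the covariate and 3 hours the outcome, there is no dilution. Items 9 and 20 of the first run contain no contrast of ticagrelor with none, although half of the AUC in item 20 precedes ticagrelor.

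**Is the loss larger?** Setting the AUC against a covariate-adjusted 3-hour value gives 2/(1−ρ), or 2.9, 4.0 and 6.7 at ρ = 0.3, 0.5 and 0.7. That adds the separate gain from adjustment, a factor of 1/(1−ρ²), to the dilution. Like for like, the factor is 2(1+r).

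**Can item 9 not be run at all?** As written it cannot, but endpoint 8 and the other bleeding-time items say 3 hours. It is a slip that the plan itself resolves.

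**Is ticagrelor against none the main use of bleeding time?** Section 2 motivates the measure by comparing aspirin regimens on a ticagrelor background, so the documents do not support that either.

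**Conclusion.** The concern holds for item 10 of the monotherapy-against-combination list, with the same dilution in the main effect of item 19 and a conditional one in 10.6 item 8. Relative to the 3-hour effect, the time-averaged AUC shows exactly half. It needs 2.0 to 3.4 times as many pairs as the unadjusted 3-hour value for r from 0 to 0.7, which is an assumed range, with equal SDs at the two times.

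Half is not the loss against every alternative. Against an AUC whose time 0 came after dosing, the share retained is 1/(1+f), where f is the fraction of the 3-hour effect already present one hour after dosing: 50% at f = 1, 57% at 0.75 and 67% at 0.5. The documents give no f, so for f between 0 and 1 a half is the worst case.

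This is one secondary endpoint. The fault costs sensitivity and does not itself create false positives. The primary TNF-α analysis is untouched. It should be corrected, together with the 6-hour entries.

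**What to change.** - **Ticagrelor contrast (second run, item 10).** Replace the AUC by the 3-hour bleeding time, compared within participant and adjusted for that day's pre-dose value, or as the change from it. Change has variance 2s²(1−r), so it beats the plain 3-hour difference only if r exceeds 0.5; adjustment is the safer choice.
- **Item 19.** Read the ticagrelor effect from the interaction with time, not from the main effect.
- **10.6 item 8.** Make 3 hours the outcome and name the covariate. Take aspirin coefficients from a model with the visit 2 value. If the same-day value is used, read only the ticagrelor coefficient from that model.
- **Between aspirin regimens (first run, items 9 and 20).** Use the 3-hour value with the visit 2 bleeding time as covariate. Do not adjust for the same-day pre-dose value: it follows 10 to 14 days of allocated aspirin, and adjusting for it would remove part of the effect under study.
- **Time points.** Change 0 and 6 hours to 0 and 3 hours for bleeding time (first run, item 9) and for aggregation (first run, item 10; 10.6 item 9). Reconcile the 0 to 6 hours of endpoint 9 with the 3-hour sampling. Take time 0 for aggregation from the sample after dosing and before endotoxin.

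The edits reach Protocol 3.3 and section 10 as well as the SAP. The cost is the redefinition of one secondary endpoint, best settled before bleeding time is compared by treatment. No sample, visit or dosing step changes.
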